### **End of the Trial**

The end of the study will be on the last participant visit. The end of the study overall will be when the results will be written up and publication submissions will be attempted.

## **Selection and Withdrawal of Participants**

### **Recruitment**

There are several potential recruitment pathways for this study:

- 1) A selection of eligible people for the study will be invited from existing databases (Knee Pain in the Community (KPIC) and Investigating MSK Health and Well-being (IMH&W) Databases) held at Academic Rheumatology of participants with knee pain who have agreed to be contacted for future studies. The databases can be accessed by a member of the research team who will also contact the potential participants to ask if they are interested. We aim to recruit 140 participants and out of those we also aim to recruit 25 to participate in the sub-study.
- 2) Participants will also be recruited from consultant waiting lists and clinics for Total Knee Arthroplasty (TKR) at Nottingham University Hospitals NHS Trust. An invitation pack will be posted to eligible participants who are on the waiting list for TKA, these pack will be sent by the participants treating orthopaedic surgeons or a member of their administrative team. Interested individuals will be invited to declare their interest by mailing their reply slip via a prepaid envelope directly to the study team.

The study team in Academic Rheumatology will phone interested participants to further establish eligibility and to screen them about x-ray scanning. From those who had an x-ray in the previous 12 months and their x-ray was undertaken within the Nottingham University Hospital (NUH) Trust, verbal consent will be requested over the phone for a member of the study team with an honorary contract with NUH to access the relevant-only information in order to establish whether the existing scan is relevant to this research.

Study visits will take place either in the Clinical Sciences Building in Academic Rheumatology, or in an NHS clinic room at the Queens Medical Centre site. Participants who satisfy the eligibility criteria upon the telephone screening will be invited to attend a study visit, at a day of their convenience. That visit will be considered as their single study session. The purpose of the visit will be to further establish suitability and gain full consent about knee aspiration and all other proceedings (samples, ultrasound, functional assessment) before any study activities are undertaken. Participants will be eligible for inclusion to the study if they are willing to undergo knee synovial fluid aspiration and demonstrate radiographic evidence of osteoarthritis (K/L= 1 or above) or if they satisfy the American College of Rheumatology clinical criteria for knee OA (139) even in the absence of radiographic findings (e.g. knee pain and three or more of the following: over the age of 50, less than 30 minutes of stiffness in the morning, no palpable warmth on synovium, bony tenderness, bony enlargement, crepitus on active motion).

Participants will be free to leave the study at any time without giving any reason. Participants who indicate in their questionnaire that they are willing to receive information about future knee pain studies may withdraw this indication at any time, and this will be altered appropriately on the study database. Participants will be made aware via the questionnaire that all data will remain confidential and will be anonymised before use in further analysis.

It will be explained to the potential participant that entry into the study is entirely voluntary and that their treatment and care will not be affected by their decision. It will also be explained that they can withdraw at any time, but attempts will be made to avoid this occurrence. In the event of their withdrawal, it will be explained that any data collected so far cannot be erased, and we will seek consent to use the data in the final analyses where appropriate (via the information sheet and consent form). Those who withdraw from the study will be made aware that this will not in any way affect their future care.

Participants who have agreed to participate in the study will be asked directly by a member of the research team whether they would like to participate also in the sub-study. Those who will agree to participate will be provided with a separate Participant Information Sheet (PIS) composed specifically for the sub-study and they will have to sign an additional informed consent form (ICF).

### **Inclusion criteria**

For individuals to be included in the study they must:

- have the ability to give informed consent
- be 45 years or over
- have complaints of knee pain for 3-6 months with or without radiographically established OA (K/L scale score  $\geq 1$ )
- have complaints of knee pain for 3-6 months with or without satisfying the non-radiographic American College of Rheumatology criteria for knee OA
- are willing to undertake knee synovial fluid aspiration

- be able to speak, read, and write in English as all instructions and questionnaires are designed in the English language

### **Exclusion criteria**

Individuals who meet one or more of the following criteria will be excluded:

- Inability to give informed consent due to cognitive impairment or otherwise – (capacity levels are already established under GP care)
- Inability to understand key aspects of the study due to cognitive impairment or otherwise
- Giving history of additional co-morbidities such as cancer, neurological conditions, inflammatory joint diseases including rheumatoid arthritis, diabetic neuropathies, fractures or other conditions causing greater disability than their knee pain
- Acute soft tissue injury to the knee within last 3 months before potential recruitment

### **Participant Withdrawal**

Participants may be withdrawn from the study either at their own request or at the discretion of the investigator. The participants will be made aware that this will not affect their future care. Participants will be made aware (including via the information sheet and consent form) that should they withdraw the data collected to date cannot be erased and may still be used in the final analysis.

### **Informed consent**

All participants will provide written informed consent. The ICF will be signed and dated by the participant before they enter the trial. The Investigator will explain the details of the trial and provide a Participant Information Sheet, ensuring that the participant has sufficient time to consider participating or not. The Investigator will answer any questions that the participant has concerning study participation.

Informed consent will be collected from each participant before they undergo any interventions (including physical examination and history taking) related to the study. One copy of this will be kept by the participant, one will be kept by the investigator, and a third will be retained in the participant's hospital records.

The same process will be reiterated with a separate study specific information sheet and consent form for those individuals who will agree to participate in the sub-study and undergo the additional assessment.

Should there be any subsequent amendment to the final protocol, which might affect a participant's participation in the study at any part, continuing consent will be obtained using an amended Consent form which will be signed by the participant.

### **Future contact**

The consent form includes an optional clause asking participants to confirm whether they are happy for their personal details to be retained in order to be informed about relevant future studies within the Pain Centre for which they might be suitable. If they consent, their data will be stored on a secure database on a University of Nottingham server and will be kept up-to-date in accordance with Data Protection Act, 2018. If not, their contact details will be destroyed at the end of this study after it is no longer necessary to contact them.

## **Study Regimen**

Participants seeking care for their knee pain will be informed of the study both orally and in writing. Those who qualify for the study will be asked to come to Academic Rheumatology for a single session. All research activities will be undertaken on the same session which is expected to last no longer than 2 hours. During the single session, participants will sign the informed consent form (ICF) and will be asked to go through the study procedure. All participants will have blood samples extracted. All participants will have a knee ultrasound scan by a trained member of the study team to assess their knee and locate the best needle insertion point and go through the ultrasound-guided aspiration (USGA) procedure. Participants will then have their pain sensitivity, strength, balance and function measured by special tests (sit to stand, time up and go). Outcome measures about pain mechanisms (CAP-Knee), OA (WOMAC), cognitive function (CFQ), frailty (FRAIL), and health (EQ5d-5L) will be completed by participants at home online or on paper copies. Participants will be also asked if they wish to donate a faecal sample and if they agree they will be given a collection kit to take home along which will be shipped back by post.

To summarise, the total study duration, including recruitment and the assessment visit, will be 18 months. The key stages are detailed below:

- Individuals who agree to attend for a clinical assessment will participate for a single appointment. This appointment will last approximately 2 hours.
- They will be seen at the Academic Rheumatology Unit, Clinical Sciences Building, Nottingham City Hospital or in an NHS clinic room at Queens Medical Centre.
- Transport (taxi) will be arranged if required and any travel expense will be reimbursed.
- Our Research Nurses will get a 15ml blood sample from the participant
- Once blood samples have been collected participants may be offered a light breakfast and drink refreshment before a brief assessment to confirm medical history and current medications.
- Questionnaires such as WOMAC, EQ5D-5L, CFQ, CAP-Knee, FRAIL and Numeric VAS will be collected.
- Physiological measurements such as 30 seconds sit to stand (30CST), time up and go (TUG), balance and muscle strength assessments will be taken at this point.
- Diagnostic ultrasound of the most painful knee will be conducted and ultrasound guided synovial fluid aspiration will follow.
- Follow up questionnaire will be posted or conducted through the telephone in line with the questionnaires at the initial visit.

## **Muscle, Strength, and Balance Measurements**

A sequence of four physiological measures will be undertaken:

**Time up and Go:** The participant will start in a seated position. The participant will stand up upon therapist's command, walk 3 meters, turn around, walk back to the chair and sit down. The time will stop when the participant is seated. The subject can use an assistive device. If the assistive device is used, it will be documented.

**NOTE:** A practice trial will be completed before the timed trial

**30 seconds sit to stand.** The 30-Second Chair Test is administered using a folding chair without arms, with a seat height of 17 inches (43.2 cm). The chair, with rubber tips on the legs, is placed against a wall to prevent it from moving. The participant is seated in the middle of the chair, back straight; feet approximately shoulder width apart and placed on the floor at an angle slightly back from the knees, with one foot slightly in front of the other to help maintain balance. Arms are crossed at the wrists and held against the chest. Demonstrate the task both slowly and quickly. Have the participant practice a repetition or 2 before completing the test. If a participant must use their arms to complete the test, they are scored 0. The participant is encouraged to complete as many full stands as possible within 30 seconds. The participant is instructed to fully sit between each stand. While monitoring the participant's performance to ensure proper form, the tester silently counts the completion of each correct stand. The score is the total number of stands within 30 seconds (more than halfway up at the end of 30 seconds counts as a full stand). Incorrectly executed stands are not counted. The 30-second chair stand involves recording the number of stands a person can complete in 30 seconds rather than the amount of time it takes to complete a pre-determined number of repetitions.

**Muscle strength Assessment:** Isometric testing will be done at 30 and 60 degrees of flexion as done in the previous study and the participant will be in sitting position with hips and knees strapped to keep the position standardised.

**Balance:** Static balance and postural sway either in the medial-lateral or antero-posterior direction will be assessed using the RS Scan force plate. The participant will be asked to stand on the plate looking straight forward for 30 seconds in two conditions: first with their eyes open and then with eyes closed. Medial-lateral, antero-posterior and total sway will be recorded.

### **Ultrasound & Ultrasound-guided Aspiration**

During the ultrasound scan, the supra-patellar pouch, medial and lateral recess of the knees will be assessed for synovial thickening, synovial fluid/effusion and for positive power Doppler. An ultrasonic probe will be used to direct ultrasonic waves onto the knee joint during sonography, and a computer converts the signals received so that they can be presented on the screen. During skin application, a sterile probe cover and sterile acoustic gel will be used. There is no radiation exposure to ultrasound due to the lack of radioactive rays and no detrimental side effects.

Once the best aspiration location is identified and the location of the needle insertion marked, the skin will be prepared with a cleansing agent such as iodine or chlorhexidine. The needle may be introduced into the skin either parallel to the probe or perpendicular to the probe (Figure 1). When the needle runs parallel to the probe it will be seen in full length. If it is advanced perpendicular to the probe the needle is only represented by a hyperechoic spot in the ultrasound image.

[figure not shown]

Figure 1. Approaches of ultrasound guided injections with possible positions of needles and probes (141).

Once the aspiration is completed, the needle will be removed, the skin cleansed, and a bandage will be applied. A woven elastic bandage or knee immobilizer may be applied to reduce post-procedural swelling and discomfort (140).

### Compliance

Compliance will be judged by attendance for study-related appointments and during the study visit based on completion of key study procedures. Participants will be replaced only if they refuse to undertake ultrasound-guided synovial fluid extraction and quantitative sensory testing. Individuals will be given a contact number to contact us if they have any query or wish to reschedule an appointment.

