## SYNOPSIS

Title	Molecular pathways involved in knee pain: an observational study
Short title	Molecular pathways involved in knee pain
Chief Investigator	[name] [name]
Objectives	
Observational Study:
 
[1] To test whether there is an association between proteomic concentrations in the synovial fluid and pain hypersensitivity.
 
[2] To identify proteomic signatures in synovial fluid of centrally vs peripherally driven knee pain.
 
[3] To investigate the relationship of pain hypersensitivity and different proteomic profiles with radiologically-established joint structural changes and muscle strength.
 
[4] To explore the correlation between knee inflammation (effusion, synovial hypertrophy or/and synovial hyper vascularity) and biomarkers of insulin resistance, stress, DNA markers, poor metabolism and knee pain.

Study Configuration	Observational cross-sectional study
Setting	University and secondary care
Sample size estimate	
Observational Study: We propose to compare proteomic signatures in 140 knee pain cases. To achieve a Bonferroni <math>p < 1.25 \times 10^{-5}</math> (adjusting for 4000 tests, i.e. the number of proteins in the Somalogic platform) effect sizes of <math>\beta=0.64</math> in units of standard deviations are needed to achieve 80% statistical power. Based on the effects seen on radiographic progression (standardized <math>\beta=0.62</math>) these effects appear reasonable and achievable with the proposed sample size.
 
Reliability Sub-study: Considering that the study will comprise two different sessions (<math>n=2</math>) featuring one measurement within each and with minimally accepted reliability of <math>p_0=0.5</math> and expected reliability of <math>p=0.8</math>, the minimum sample size has been calculated to be 22 participants. High variability is not expected however, to account for such an occurrence, data will be collected from 25 individuals.

Number of participants	Observational Study: 140 Sub-study: 25
Eligibility criteria	
Inclusion criteria:
 
 
• have the ability to give informed consent
 
• be 45 years or over
 

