## STUDY BACKGROUND INFORMATION AND RATIONALE

Osteoarthritis (OA) is the most common cause of disability in the elderly population and most individuals suffering from osteoarthritis are managed in the primary care setting (1). Knee OA is the most common form of arthritis and the most common cause of knee pain in the world (2). The rate of knee arthritis is as high as that of cardiac disease and is the most common problem in individuals over the age of 65 (3). In the United Kingdom, 10% of 65 to 74-year-old individuals consult their general practitioners about OA per year (4). Out of the entire population, 4% attend their general practitioners as a result of knee OA, and half of them (2%) consult their general practitioner for the first time or with the acute flare of knee arthritis (1).

We will recruit 140 individuals with OA-related knee pain, and we will record their pain levels on the Numerical rating scale (NRS) at a single time-point. The validity and sensitivity of NRS have been established numerous times (14-18).

Metabolic evidence from body secretions can provide significant insight about the course of OA, as the presence of glucosamine and chondroitin sulfate in faecal samples has shown to improve the symptoms of the condition and delay its progression (56). Nutritional information and metabolic evidence from faecal samples can be used to explore associations of gut microbiota with pain sensitivity and stress levels (57, 58).

The widely utilised Western Ontario and McMaster Universities Osteoarthritis Index (WOMAC) will be also used for the evaluation of knee OA. It is a self-administered questionnaire made of 24 items and consists of three subscales covering pain, stiffness and physical function. It has been used extensively and is considered a valid and reliable tool (59-63). Frailty has been also found to be a predictor of disability (66) and a determinant of treatment outcomes (67-69) and the Simple Frailty Questionnaire (FRAIL) is considered a valid and reliable tool for that purpose (70).

Both the 30-second sit to stand test (30CST) and the 'time up and go' (TUG) test will be used to see if patients have improved their lower limb fitness levels. 30CST has shown excellent reliability and validity (63, 71, 72). TUG has been widely used in clinical setups and is a valid tool to assess necessary functional mobility (73-79).

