Musculoskeletal Ultrasound scan (MSK-USS) will be also conducted on the knees of participants to establish if they have inflammation of the synovial membrane. There is enough evidence that inflammation is present in all stages of OA (108-111). Synovitis or inflammation of synovial fluid is associated with pain, disease severity and, OA progression (108, 112). Synovitis manifests as synovial membrane thickening, increased vascularity, and/or joint effusion (108, 113-115). During MSK-USS, the presence of synovial fluid, synovium hypertrophy, and Power Doppler will be also assessed. Synovial hypertrophy, synovitis and knee effusion are linked with arthritis in the knee and associated with knee pain in osteoarthritis (116-121). Power Doppler provides a reliable and accurate method for visualising blood flow in the synovial tissue, and histological findings support the value of this technique (119, 122, 123). An ultrasound scan is considered to be a valid and reliable instrument for the assessment of synovial disease (113, 119, 120, 124) and synovitis is strongly associated with osteoarthritis as mentioned earlier. The synovial fluid will be aspirated (subject to participant consent), in order to establish a phenotype which is strongly associated with OA. Studying synovial fluid biomarkers alongside clinical, radiographic and ultra-sonographic characteristics is one strategy to improve resolution and stratification into targetable OA phenotypes (125). Synovial fluid aspiration will be ultrasound guided as it increases the accuracy of needle placement

compared to blind needling (95.8% versus 77.8%,  $p < 0.001$ ) (126) reduces procedural pain by 43%, improves effusion detection by 200%, and volume of synovial fluid aspirated by 337% compared with blind synovial fluid aspiration (127). Ultrasound guidance also reduces procedural pain (43% reduction) in knees with no palpable effusion and increases the responder rate and therapeutic duration by 107% and 36% respectively (128-132).

Optionally, isometric quadriceps strength will be also assessed to establish current strength levels of vastus medialis muscle and see whether muscle strength associates with centrally driven pain or proteomic synovial concentrations. Quadriceps muscles strength deficits are associated with knee osteoarthritis (133). Isometric testing will be done at 30 and 60 degrees of flexion as per the protocol of a previous study (134). Hand grip strength will also be measured as an option

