## **STATISTICS**

### **Methods**

The chief investigator, co-investigators and the study statistician will evaluate the findings and analysis will be carried out by the co-investigator. The data will be entered into MS Access and analysed using with STATA, SPSS (Statistical Packages for Social Scientists, version 19) and R software. Data will allow exploration of potential relationships between objective sensory measures and molecular findings and/or pain. Several factors that putatively mediate the primary or secondary outcomes are inter-correlated so investigation of their interaction must be ascertained. Simple univariate unadjusted correlations (Pearson/Spearman) and linear regression modelling will be used to examine associations between pain and molecular findings in the synovial fluids at baseline. Multiple linear

regression (MLR) modelling (backward stepwise regression) will be conducted to assess the impact of the significant independent variables and their interactions with the dependent variable.

The results of the study will be available to the study management group. All data will be stored in Academic Rheumatology and will be backed up on the University of Nottingham servers.

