### **Sample size and justification**

We propose to compare proteomic signatures in 140 knee pain cases. To achieve a Bonferroni  $p < 1.25 \times 10^{-5}$  (adjusting for 4000 tests, i.e. the number of proteins in the Somalogic platform) effect sizes of beta = 0.64 in units of standard deviations are needed to achieve 80% statistical power. Based on the effects seen on radiographic progression (standardized beta = 0.62) these effects appear reasonable and achievable with the proposed sample size.

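### The power statement treats all 140 recruits as assayed synovial fluid samples, and its 80% power at beta = 0.64 does not match the planned single-cohort analysis.

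*Combined protocol and SAP*

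**What the plan says.** Three places give 140 as the number of people entering the study. The Synopsis lists "Observational Study: 140 Sub-study: 25"; the Recruitment section says "We aim to recruit 140 participants and out of those we also aim to recruit 25 to participate in the sub-study"; the Background says "We will recruit 140 individuals with OA-related knee pain".

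The Sample size and justification section uses the same figure as the number with proteomic data: "We propose to compare proteomic signatures in 140 knee pain cases". It sets a Bonferroni threshold of p < 1.25e-5 for 4000 proteins and states that "effect sizes of beta = 0.64 in units of standard deviations are needed to achieve 80% statistical power". It does not name the model, the sidedness or a loss allowance.

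The Recruitment and Inclusion criteria sections require willingness to be aspirated, not an effusion or an obtained sample. On replacement, the Compliance section says: "Participants will be replaced only if they refuse to undertake ultrasound-guided synovial fluid extraction and quantitative sensory testing".

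For the analysis, the Methods section says that simple correlations and "linear regression modelling will be used to examine associations between pain and molecular findings in the synovial fluids at baseline". It defines no proteomic analysis set and no handling of participants without a sample.

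**The concern.** There are two linked problems and one smaller one.

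- **The number analysed.** A willing participant whose knee yields no usable fluid, or whose sample fails in the laboratory, is enrolled and, on the wording of the replacement rule, not replaced. No sentence says this outright; it follows from the rule and the entry criteria together. The 140 then holds for the primary objective, secondary objective 1 and the proteomic part of secondary objective 3 only if every aspiration and assay succeeds. Relations of pain with radiographs, strength, ultrasound and blood markers need no fluid and are unaffected.
- **The power figure.** Without a named model, a reader cannot tell whether lost samples are harmless or serious. The stated combination of 140, 0.64 and 80% does not correspond to the analysis in the Methods section.
- **Possible selection.** The Background states: "Synovial hypertrophy, synovitis and knee effusion are linked with arthritis in the knee and associated with knee pain in osteoarthritis". If fluid is easier to obtain from knees with effusion, participants with proteomic data may differ in pain, the primary endpoint, from those without. The plan does not say this will be described or checked.

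**Working it through.** **Inputs from the documents.** N = 140; 4000 tests; beta = 0.64 SD; power 80% (Sample size and justification). Correlation and linear regression in one cohort (Methods). **Assumptions.** Two-sided testing; losses of 10%, 20% and 30%, since no yield is given. The Background's 95.8% is needle placement accuracy, and its other aspiration figures are comparisons with blind aspiration, so none serves as a yield.

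**Step 1: threshold.** 0.05/4000 = 1.25e-5, as stated. Two-sided z = 4.369; z for 80% power = 0.842; sum 5.210.

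**Step 2: try to reproduce 80% at 0.64 with 140.**

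- *Regression slope, predictor SD 1, residual SD 1.* Noncentral t, 138 df, noncentrality 0.64 × √140 = 7.57. Power is 99.8%. About 76 samples already give 80%.
- *Correlation (both variables standardised), Fisher z.* atanh(0.64) = 0.758. Power at 140 is Φ(0.758 × √137 − 4.369), above 99.9%. For 80%, n = (5.210/0.758)² + 3 = 50.2, so 51.
- *Two groups of 70.* Normal approximation: Φ(0.64 × √(70/2) − 4.369) = 28%. Noncentral t: 24%.
- *Two groups of 140 (280 in total).* Noncentral t: 81.4%; about 138 per group give 80%.

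Of these readings, only the last comes close to the stated figure, and it needs twice the planned recruitment.

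**Step 3: what the planned analysis can detect with 80% power.** For the correlation, r = tanh(5.210/√(n − 3)). The slope is solved from the noncentral t with predictor and residual SD 1.

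| Assumed loss | Assayed | Detectable correlation | Detectable slope | Power at slope 0.64 |
|---|---|---|---|---|
| 0% | 140 | 0.42 | 0.46 | 99.8% |
| 10% | 126 | 0.44 | 0.48 | 99.4% |
| 20% | 112 | 0.46 | 0.51 | 98.2% |
| 30% | 98 | 0.49 | 0.55 | 95.1% |

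The last column treats the predictor as fixed. Treating it as random lowers power at 98 samples to about 93%.

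The two effect columns are not interchangeable. If pain and protein are both standardised, the slope equals the correlation and the correlation column applies. The slope column needs residual SD 1.

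**Step 4: the replacement rule.** Read literally, its *and* requires refusal of both aspiration and quantitative sensory testing. The Secondary endpoint list, the Study Regimen, the Muscle, Strength, and Balance Measurements section and the Methods name no such test, although the Study Regimen mentions pain sensitivity and the Methods mention objective sensory measures.

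**The case against.** The strongest reply is that nothing is lost. Under the regression in the Methods section, 76 samples suffice for a slope of 0.64, so even a loss of about 45% (140 down to 76 or 77) leaves roughly 80% power. Using only participants with fluid in the proteomic models, and everyone in the rest, is the ordinary consequence of the planned regressions. That stands as far as power is concerned.

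A reader might infer the opposite: that power starts at 80% with 140 samples and falls steeply with each lost sample. The documents do not support this. No identified test gives 80% at 0.64 with 140 in total, so there is no valid baseline to scale down from.

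A reader might also infer that the proteomic subset will be selected on pain. The documents associate effusion with pain but do not say that obtaining fluid depends on effusion, and they describe benefits of ultrasound guidance in knees without palpable effusion. Selection is possible, not established.

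What the reply does not answer is that the power paragraph is wrong for the planned analysis, uses a sample count that the entry and replacement rules do not secure, and leaves open whether a group comparison was intended. Its verb is *compare*, and the second Synopsis objective contrasts centrally with peripherally driven pain.

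**Conclusion.** The point holds in a limited form. The 140 in the power statement is a recruitment count, and any failed aspirate or assay reduces the number analysed; by how much cannot be said from the documents. The stated 80% at 0.64 does not describe the planned single-cohort analysis, for which 140 samples give 80% power at a correlation of about 0.42 or a slope of about 0.46. It fits only about 140 per group; two groups of 70 would give about 24–28%.

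No power shortfall is shown for the planned analysis. At assumed losses of 10% to 30%, the detectable correlation is 0.44 to 0.49 and the slope 0.48 to 0.55, all below 0.64. These figures rest on two-sided testing, on the scaling named for each and, for the slope, on a predictor treated as fixed. The case for change is that the paragraph should match the analysis and the samples available, and that a possible selection can be checked with data already being collected.

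**What to change.** 1. Keep 140 recruited. Restate the power paragraph for the expected number of assayed samples, giving the assumed yield and its basis, the model, the sidedness, the scaling (both variables standardised, or residual SD 1) and the detectable effect from the matching column above. Make the same change in the Synopsis.
2. If a comparison of centrally with peripherally driven pain is what was powered, state the group sizes and the power they give.
3. State that participants without an assayed sample stay in the analyses that need no fluid. Report the numbers recruited, aspirated, yielding fluid and assayed.
4. Compare pain and ultrasound effusion between participants with and without an assayed sample.
5. Separately, reconcile the sensory-testing condition in the Compliance section, including its *and*, with the Secondary endpoint list, the Study Regimen, the Muscle, Strength, and Balance Measurements section and the Methods.

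The cost is revised text, four counts and one comparison on data already collected. No extra recruitment or procedure is needed; replacing failed samples to reach 140 assayed is optional. The downside is a little extra analysis and a changed power figure. For the single-cohort analysis at these assumed yields, the detectable effect is smaller than 0.64. If two groups within the 140 were intended, the restated power would be much lower than 80%.
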